6 STUDY SETTING

The study will be performed in the Wellcome Trust-NIHR Clinical Research Facility at Addenbrooke's Hospital. The staff and infrastructure of the CRF bring considerable expertise and experience in research involving metabolic factors and infusion of blinded agents. Each study visit will be supported by at least a dedicated nurse and doctor for the duration of the visit.

7 SAMPLE AND RECRUITMENT

7.1 Eligibility Criteria

7.1.1 Inclusion criteria

Participants must be:

- At least 3 months post completion of treatment for gastric cancer, or prophylactic gastrectomy
- Aged at least 18 years
- Able to tolerate an oral glucose tolerance test
- Able to understand and retain all information regarding the study and give informed consent.
- Willing to receive an infusion of human albumin solution

7.1.2 Exclusion criteria

Participants must not:

- Have a diagnosis of diabetes
- Have a history of untreated anaemia in the last 3 months
- Be aged under 18 years
- Have active gastric cancer
- Be pregnant or attempting to conceive

7.2 Sampling

7.2.1 Size of sample

Up to sixteen participants will be recruited for this study, each to complete one screening and two randomised study visits (placebo and Exendin 9-39). Previous data shows a between visit correlation of glucose measurement of 0.52, with standard deviation of 0.5. Salehi et al demonstrated mean nadir blood glucose of 3.9mmol/L (standard deviation 0.6) with GLP-1 blockade and 2.6mmol/L (0.6) with placebo in post-bariatric surgery patients⁵. Based on this data, we have conservatively estimated an effect size of 0.5 (based on mean change in nadir glucose of 0.5mmol/L. To detect this change with 90% power at a 5% significance level requires a sample size of 13. The recruitment of sixteen participants will allow for drop outs, and for the possibility that more data will be required to reach significance in the previously unstudied (in this group) outcomes of food motivation and reward behaviour.

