1 BACKGROUND

It is well established that surgery on the upper gastrointestinal tract profoundly alters appetite, weight and glucose homeostasis. This is harnessed in the treatment of obesity and type two diabetes¹ but can have significant deleterious effects in the lean population undergoing surgery for cancer². At present, there is no adequate understanding of the pathophysiological basis of these changes, although it is suspected that gut hormones, bile acids and neuro-cognitive factors may play a role^{3,4}.

Approximately 2500 gastric and oesophageal resections are carried out annually in the UK for cancer, with a 50% five year survival rate. Long-term quality of life after gastrectomy is known to be poor, with a high prevalence of “dumping syndrome”, a poorly understood constellation of symptoms². There is no effective treatment, or indeed understanding of the underlying cause, of these symptoms. This is a significant unmet need in the field of cancer survivorship.

The role of the (Glucagon-like-peptide-1) GLP-1 – insulin axis in the resolution of obesity and diabetes after bariatric surgery has been studied by several groups, and is suspected to play a role in the severe hypoglycaemias seen by some patients⁵. No one to date has assessed the role of GLP-1, a gut derived hormone responsible for potentiating the insulin response and suppressing appetite, in the symptoms seen after gastrectomy for cancer. A pilot study run by our group has demonstrated significantly elevated levels of GLP-1 and insulin, and altered appetite and satiety responses, in a cohort of five post-gastrectomy patients. The exact physiological effect of the GLP-1 elevation is however less clear, and temporary blockade of the GLP-1 axis will allow us to define the physiological changes resulting from GLP-1 secretion versus other altered physiological pathways in this group.

This study is a double-blind, crossover physiological study of the effects of excess GLP-1 secretion on glycaemic profile and cognitive eating behaviour factors in the post-gastrectomy population.

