3 THEORETICAL FRAMEWORK

We hypothesize that blockade of the GLP-1 axis using Exendin 9-39 in the post-gastrectomy population will:

1. Ameliorate the excessive post-prandial insulin response seen in this patient group, as evidenced during a 50g oral glucose tolerance test by:
 - a. Increased nadir blood glucose
 - b. Reduced total insulin secretion
2. Ameliorate the increased satiety signalling and consequent effects on food intake, hunger and satiety, and food motivation during and after an ad libitum meal, as evidenced by:
 - a. Increased eating rate and food intake during ad libitum meal
 - b. Increased hunger and decreased satiety ratings during and immediately after the ad libitum meal
 - c. Increased attention to and motivation for food both prior to and after the ad libitum meal

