7.2.2 Sampling technique

Participants will be sampled from all patients under follow up after total gastrectomy by the Cambridge Oesophago-gastric centre at Addenbrooke's Hospital, or known to the service through the Familial Gastric Cancer Study (provided they have indicated an interest in being contacted regarding future research). We will select participants with suspected or proven post-prandial hypoglycaemia based on oral glucose tolerance tests performed as part of clinical care or other research projects administered by our study team.

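### Does the stated 90% power with 13 participants rest on the wrong standard deviation for nadir glucose?

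*Combined protocol and SAP*

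**What the plan says.** Section 7.2.1 builds the calculation in four steps.

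- **Variability:** "Previous data shows a between visit correlation of glucose measurement of 0.52, with standard deviation of 0.5". No citation, population or time point is given.
- **External evidence:** a cited post-bariatric study with "mean nadir blood glucose of 3.9mmol/L (standard deviation 0.6) with GLP-1 blockade and 2.6mmol/L (0.6) with placebo".
- **Target:** "Based on this data, we have conservatively estimated an effect size of 0.5 (based on mean change in nadir glucose of 0.5mmol/L".
- **Result:** "To detect this change with 90% power at a 5% significance level requires a sample size of 13".

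On the recruitment target it adds: "The recruitment of sixteen participants will allow for drop outs, and for the possibility that more data will be required". The further data are wanted for the food motivation and reward outcomes. The outcome used for sizing matches hypothesis 1a in section 3, "Increased nadir blood glucose". Neither the test nor its sidedness is stated.

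Two other places show that the group holds data of its own. Section 1 describes a pilot that found raised GLP-1 and insulin and "altered appetite and satiety responses, in a cohort of five post-gastrectomy patients". Section 7.2.2 on sampling technique refers to "oral glucose tolerance tests performed as part of clinical care or other research projects administered by our study team". Section 7.2.1 names neither as the source of the SD or the correlation.

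**The concern.** The target is a change in nadir glucose, but the SD of 0.5 and the correlation of 0.52 are described only as belonging to a glucose measurement. The one SD explicitly tied to nadir glucose is 0.6 in both conditions, and it stands in the very next sentence. The plan calls its target conservative, yet it uses the smaller of the two SDs without saying why.

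Nadir glucose is the only outcome with a stated power. If 0.6 were the right SD and the correlation were still 0.52, the chance of missing a true 0.5 mmol/L change with 13 completers would be about 20%, not 10%. The three extra participants would no longer cover drop-outs, because even 16 completers fall slightly short of 90%.

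The term effect size adds to the doubt. Read as a standardised effect, 0.5 would need 43 or 44 participants, and 13 would look far too few.

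**Working it through.** **Inputs.** From section 7.2.1: difference 0.5 mmol/L, SD 0.5, correlation 0.52, significance level 5%, target power 90%. From the cited study in the same section: SD 0.6, and a difference of 3.9 − 2.6 = 1.3 mmol/L. Assumed: a two-sided paired t-test, with power from the noncentral t distribution on n − 1 degrees of freedom.

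**Formulas.** SD of the within-participant difference = SD × √(2 × (1 − correlation)). Standardised paired effect = difference / SD of the difference. Noncentrality = standardised effect × √n.

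**1. The plan's own figure.** SD of the difference = 0.5 × √(2 × 0.48) = 0.490. Standardised effect = 0.5 / 0.490 = 1.02. Power is 89.5% at n = 12, 92.1% at 13 and 96.8% at 16. The smallest n with at least 90% is 13, as stated. Other methods do not give 13: the normal approximation gives 10.09, rounded up to 11, and a one-sided t-test gives 10. Allowing one more degree of freedom for a period effect (n − 2) still leaves 91.7% at 13.

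**2. Other reading of the SD.** If 0.5 is the SD of the between-visit difference, the required n is again 13, with 91.1% power. The implied SD per condition is then 0.5 / √0.96 = 0.51.

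**3. SD 0.6, correlation 0.52.** SD of the difference = 0.6 × √0.96 = 0.588. Standardised effect = 0.5 / 0.588 = 0.85.

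| Completers | 13 | 14 | 15 | 16 | 17 |
|---|---|---|---|---|---|
| Power | 80.4% | 83.7% | 86.5% | 88.8% | 90.8% |

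With n − 2 degrees of freedom, power is 79.7% at 13 and 88.5% at 16. The difference detectable with 90% power is 0.58 mmol/L at 13 and 0.51 mmol/L at 16.

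**4. Dependence on the correlation, at SD 0.6.** The documents give no correlation measured alongside the 0.6, so this range is assumed.

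| Correlation | Power at 13 | Power at 16 | n for 90% |
|---|---|---|---|
| 0.30 | 64.5% | 75.0% | 24 |
| 0.40 | 71.2% | 81.2% | 21 |
| 0.52 | 80.4% | 88.8% | 17 |
| 0.54 | 82.0% | 90.1% | 16 |
| 0.60 | 86.9% | 93.6% | 15 |
| 0.64 | 90.1% | 95.6% | 13 |
| 0.70 | 94.4% | 98.0% | 12 |

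**5. Larger differences, at SD 0.6 and correlation 0.52.** For 0.65 mmol/L, half the cited difference, power at 13 is 95.5%. For the cited 1.3 mmol/L it exceeds 99.9%.

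**6. Are 0.5 and 0.6 really different?** The documents do not give the size of the cited study. Assuming 8 to 30 participants and normal data, a 95% interval around an SD of 0.6 runs from 0.40–1.22 (n = 8) to 0.48–0.81 (n = 30). Both intervals contain 0.5.

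**The case for a change.** The best case for a change is that it costs one paragraph. The plan is cautious on one input (0.5 against the cited 1.3 mmol/L) and favourable on another (SD 0.5 against 0.6), and it explains only the first. Naming the source, giving the power under both SDs and writing mean difference in place of effect size would let a reader judge the claim, with no extra participants.

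Part of this stands. The source of the two inputs is missing, and so is a statement that they were measured on nadir glucose. A sensitivity line would have been informative.

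The rest is weaker. The 80% and 89% figures join an SD from one population to a correlation from the very data criticised as unsourced, and they leave out the difference that came with that SD. The paragraph does apply its earlier data to a nadir target, and section 8.1 says the group has already run glucose tolerance tests in this population, so figures from the right patients are plausible, though not confirmed. The term effect size is defined in mmol/L within the same sentence, and only that reading gives 13. Writing a two-sided paired t-test into the power statement would also commit the protocol to a test that it does not now name.

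**Conclusion.** No change is needed. The stated sample size is correct for its stated inputs: 13 gives 92.1% power and 16 gives 96.8%, assuming a two-sided paired t-test.

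The alternative of 80.4% at 13 and 88.8% at 16 holds only if the SD of nadir glucose in gastrectomy patients is 0.6 and the between-visit correlation is 0.52. The documents establish neither. They do not rule out a lower correlation with the larger SD either, so the true power could be below 80%; equally, they do not show the plan's figure to be wrong.

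Even if SD 0.6 and correlation 0.52 are accepted, full recruitment falls about one percentage point short of 90%, which gives no reason to alter a target of up to 16. The planning SD also plays no part in the analysis, where precision comes from the observed within-participant differences. What remains is an unnamed source and a loosely used term. Neither changes the design, the analysis or the way the result will be read.

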7.2.2 Sampling technique

Participants will be sampled from all patients under follow up after total gastrectomy by the Cambridge Oesophago-gastric centre at Addenbrooke's Hospital, or known to the service through the Familial Gastric Cancer Study (provided they have indicated an interest in being contacted regarding future research). We will select participants with suspected or proven post-prandial hypoglycaemia based on oral glucose tolerance tests performed as part of clinical care or other research projects administered by our study team.

7.3 Recruitment

Participants will be identified as having post-prandial hypoglycaemia (based either on symptoms or a previous glucose tolerance test) and initially approached by clinicians or clinical researchers involved in their care. If they are interested in receiving further information regarding the study, they will be contacted by a member of the study team. They will be provided with written information on the study, and if they wish to proceed, be invited to attend the CRF for a screening visit, at which time they will be formally consented by a member of the study team.

Participants will be paid an honorarium of £30 for each infusion visit (in line with current practice in our unit), and be fully reimbursed for travel costs.

7.3.1 Sample identification

Participants will be identified as meeting the inclusion / exclusion criteria by a clinician involved in their care, if necessary in discussion with the CI, who is a member of the clinical team of the Cambridge Oesophago-Gastric centre.

7.2.2 Consent

Participants will be asked to give written consent using a standard consent form at the time of the screening visit. They will be provided with written literature regarding the study prior to this occasion, and will have adequate time to ask questions, and withdraw consent should they wish. Only participants able to give fully informed consent will be recruited to this study, with capacity assessed by a clinically trained member of the study team.

8 ETHICAL AND REGULATORY CONSIDERATIONS

8.1 Assessment and management of risk

This is a physiological study, using a well described test (oral glucose tolerance test) with a blinded infusion of a peptide or placebo.

Oral glucose tolerance testing (OGTT) in this group has been carried out by our and several other groups. There is a risk of hypoglycaemia developing during the test period, for which the participant will be closely monitored using a continuous subcutaneous glucose monitor. A robust protocol is in place for the management of hypoglycaemia during an OGTT in this population, including the administration of intravenous glucose, or glucagon, should this be necessary (in our experience, this has never occurred). Other risks of the study visit and OGTT include pain and bruising at the cannulation site.

[figure not shown]
Exendin 9-39 has been used by multiple groups in Europe and the USA, with published results from 259 infusions in 240 participants^{4,8-22}. No serious adverse events have been ascribed to the use of Exendin 9-39, which is unsurprising given it is a highly selective blocker of the GLP-1 receptor with a very short half-life. It is however possible that the participant may manifest an allergic reaction to the peptide, or to the human albumin in which it is dissolved. To facilitate early diagnosis and appropriate treatment should this occur, all participants will be closely monitored by dedicated nurse and doctor during the infusion. The study will take place on a clinical research ward within Addenbrooke's Hospital, with full resuscitation equipment and access to the hospital's emergency medical team should it be necessary. The CRF has experience in running phase 1 clinical trials, including first in human studies, which carry a greater burden of risk than this proposed study.

Gastrectomy, eating behaviour and GLP-1

All adverse events (AEs) will be recorded as per the table and figure below. During study visits, participants will be questioned regarding adverse symptoms, and asked to keep a symptom diary for 24 hours post visit to ensure all AEs are recognised. All non-serious AEs will be documented and submitted in the annual safety report.

All SAEs will be reported to the sponsor within 5 working days of the investigative team being made aware of the event. SAEs will also be included in the annual safety report. The participants will have 24 hour contact details for the investigators in case a suspected SAE occurs following the study visit. In the event of a potential SAE occurring, the investigators will arrange for the participant to be reviewed promptly. Depending upon the severity of the event, the participant will be reviewed in the Wellcome Trust Clinical Research Facility (WTCRF) or will be advised to go straight to A&E (for example, if anaphylaxis is suspected).

	Expected events	All events recorded?	All events reported?	Timescale for reporting
Non-serious Adverse Event (AE)	Documented in protocol	Yes	Reported in annual study report only.	Annually in study report.
Serious Adverse Event (SAE)	Documented in protocol	Yes	Reported to sponsor within 5 working days. Reported in annual study report.	Reported to sponsor within 5 working days.

Gastrectomy, eating behaviour and GLP-1

8.2 Research Ethics Committee (REC) review & reports

- Before the start of the study, approval will be sought from a REC and the HRA for the study protocol, informed consent forms and other relevant documents.
- Substantial amendments that require review by REC will not be implemented until the REC and HRA grant a favourable opinion for the study and full R&D approval is in place
- All correspondence with the REC and HRA will be retained.
- It is the Chief Investigator's responsibility to produce the annual reports as required.
- The Chief Investigator will notify the REC and HRA of the end of the study.
- An annual progress report (APR) will be submitted to the REC and HRA within 30 days of the anniversary date on which the favourable opinion was given, and annually until the study is declared ended.
- If the study is ended prematurely, the Chief Investigator will notify the REC and HRA, including the reasons for the premature termination.
- Within one year after the end of the study, the Chief Investigator will submit a final report with the results, including any publications/abstracts, to the REC and HRA.

8.3 Peer review

Peer review has been sought from two researchers independent to the research team.

8.4 Patient & Public Involvement

A patient representative has advised on the design of this study, including acceptability of the study protocol. The concept of this study was raised at a patient and family event for the Familial Gastric Cancer population, with positive feedback on the concept of studying the causes of post-operative symptoms. The research findings will be disseminated to the interested patient groups through the bi-annual Familial Gastric Cancer workshop, and directly to any participant interested in the results.

8.5 Regulatory Compliance

- Before any site can enrol patients into the study, the Chief Investigator/Principal Investigator or designee will apply for NHS permission from the site management organisation, HEI or NHS Research & Development (R&D).
- For any amendment that will potentially affect a site's NHS permission, the Chief Investigator/ Principal Investigator or designee will confirm with that site's R&D department that NHS permission is ongoing
- The MHRA has reviewed this protocol and confirmed it does not require a clinical trial authorisation
- This study will be registered with clinicaltrials.gov for the purposes of public reporting of a study involving human participants.

8.6 Protocol compliance

Protocol compliance will be monitored by the CI, with any accidental deviations being immediately reported to CI and sponsor. Frequent deviations will be investigated by the research team and

sponsor, and if necessary the study paused for review, notification of the REC and HRA and amendments.

8.7 Data protection and patient confidentiality

The data custodian is the CI. The study and all investigators will comply with the Data Protection Act 1998 with regards to the collection, storage, processing and disclosure of personal information and will uphold the Act's core principles. Data will be managed to a written policy, with participant identifiable information stored in paper format in a locked cabinet in a secure area within Addenbrooke's Hospital. All electronic records will be anonymised and held on secure servers within the University of Cambridge, with the key held by the CI and access only granted to key clinical members of the research team. Identifiable data will be held for up to 20 years following the completion of the study (MRC guidance), with fully anonymised results uploaded to the University of Cambridge Data Repository for at least 20 years, in line with current open access requirements.

8.8 Indemnity

- 1. What arrangements will be made for insurance and/or indemnity to meet the potential legal liability of the sponsor(s) for harm to participants arising from the management of the research?*

As the co-sponsor is Cambridge University Hospitals NHS Foundation Trust, indemnity will be provided through NHS indemnity schemes

- 2. What arrangements will be made for insurance and/ or indemnity to meet the potential legal liability of the sponsor(s) or employer(s) for harm to participants arising from the design of the research?*

As the research has been designed by a substantive employee of the University of Cambridge, insurance will be sought through the University insurance policy (Ref: 609/M/C/1763).

- 3. What arrangements will be made for insurance and/ or indemnity to meet the potential legal liability of investigators/collaborators arising from harm to participants in the conduct of the research? Note that if the study involves sites that are not covered by the NHS indemnity scheme (e.g. GP surgeries in primary care) these investigators/collaborators will need to ensure that their activity on the study is covered under their own professional indemnity.*

As the research is with NHS patients on a NHS site, indemnity will be provided by NHS schemes.

No arrangements have been made for payment of compensation in the event of harm to the participants where no legal liability arises.

8.9 Amendments

Application for any future amendments will be made by the study team in line with study requirements and developments in the scientific background to the study. Amendments to the protocol will be written by the CI or a delegated study team member in discussion with the sponsor's R&D department. The decision about whether an amendment constitutes a substantial amendment will be made by the study team and

sponsor's R&D department. Amendments will be submitted to the REC and HRA through the IRAS system with all necessary amended versions of the protocol or paperwork.

All versions of study paperwork will be stored on secure University of Cambridge servers, with an amendment record stored in the appendix of the active protocol version.

